## **10.2 Treatment Exposure**

The duration of exposure (days) to study drug, total dose of ASN002, and average dose of ASN002 will be summarized using descriptive statistics (n, mean, standard deviation, median, minimum, and maximum) by treatment cohort. Duration of exposure will be calculated as the difference between the date of last administration of study drug and the date of first administration of study drug plus 1 day.

Exposure data including study drug bottle assignment, date and time of study drug administration at study site visits, diary dispense/return dates, and study drug log data will be provided in separate data listings by subject.

## **10.3 Prior, Concomitant, and Post-Treatment Medications**

Medication usage will be coded using the World Health Organization (WHO) Drug Dictionary. Medication use will be presented for the Safety population by WHO Drug Anatomical/Therapeutic/Chemical (ATC) category and WHO Drug preferred name. Medication use summaries will be presented for prior medication use (prior to first administration of study drug), concomitant medication use (between the date of first administration of study drug, but not beyond the date of the last administration of study drug), and post medication use (superseding the date of last administration of study drug). Summaries will be provided by treatment cohort and overall. Medications with partial start and/or stop dates, which cannot be definitely categorized as prior, concomitant, or post-treatment medications will be considered concomitant.

All summaries will present the number and percentages of subjects using each medication by treatment cohort. The denominators for percentages will be the number of subjects in the analysis population for the treatment cohort summarized.

Prior, concomitant, and post medications will be provided in separate data listings by subject.

## **10.4 Laboratory Evaluations**

Absolute and change from baseline values for continuous hematology panel, lipid panel, comprehensive metabolic panel, and urinalysis parameters will be summarized by analyte, assessment (see [Section 3.2](#)), and treatment cohort using descriptive statistics (mean, median, SD, minimum, maximum, and number of subjects). Categorical laboratory evaluations will also be summarized by analyte as the number and percentage of subjects at each possible analyte level. The denominators for percentages will be the number of subjects in the analysis population for the treatment cohort summarized. The following analytes will be considered for all summary tables described within this section: hemoglobin, total white

---

blood cell (WBC), WBC differential, platelets, alkaline phosphatase (ALP), ALT, AST, bilirubin, creatinine, total cholesterol, and triglycerides.

Shifts relative to baseline will be evaluated based on the Common Terminology Criteria for Adverse Events (CTCAE) v4.0 criteria and presented by analyte, assessment, and treatment cohort. Summaries will contain the numbers and percentages of subjects with sufficient data to evaluate new Grade 1 abnormalities (i.e., normal at baseline) and shifts of one Grade higher relative to baseline.

Data listings for laboratory parameters and shifts will be presented by subject.

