## 6.2 Summary of Nonclinical Studies

Nonclinical studies necessary to support clinical studies have been performed and are summarized below. Further information can be obtained from the Investigator Brochure (IB).

ASN002 showed potent inhibition of SYK and JAK kinases in biochemical assays with an IC50 range of 5-46 nM. In mechanistic cell-based studies involving IL-6 and IgE stimulation, ASN002 strongly blocks the SYK and JAK family kinase signaling pathways. The compound inhibited the proliferation of a broad range of lymphoma and solid tumor cell lines including H929, Pfeiffer, SUDHL6 and OCI-Ly10. In a multiple myeloma model (H929), ASN002 exhibited significant efficacy in inhibiting tumor growth (>95% at 90 mg/kg dose). It also delayed the onset of hind limb paralysis in the human erythroleukemia (HEL) model by nearly 33%, compared to vehicle.

ASN002 exhibits a medium to rapid rate of oral absorption, moderate to good oral bioavailability and short T1/2 in pre-clinical species. It exhibits good permeability characteristics and does not

appear to be a Pgp substrate in vitro. It is moderately bound to plasma protein and exhibits good metabolic stability in vitro. Limited metabolism may occur via 2C8, 2D6 and 3A4 pathways. Glucuronidation does not appear to be a pathway for metabolism of ASN002. ASN002 does not appear to have significant inhibitory activity on any of the CYP450 isozymes evaluated, which suggest a low potential for drug-drug interactions. Adequate systemic exposure was observed at the NOAEL in the 28-day GLP toxicology studies in both rat and dog.

The results of the mutagenicity studies suggest the genotoxic potential of ASN002 would be low. Safety pharmacology studies suggest no adverse effects on the cardiovascular (CV), CNS or respiratory systems. Decreased systolic, mean, and pulse blood pressure were observed in the dog, but the effects were reversible and can be easily monitored in the clinic.

In both the rat and dog 28-day toxicity studies, NOAELs were demonstrated. The primary toxicities in bone marrow and lymphoid tissue and were reversible. In dogs, the bile duct and gall bladder were additional target organs. One would expect hematologic changes before significant toxicity in the bile duct or gall bladder.

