#### **Non-hematologic DLT is defined as:**

Any Grade  $\geq 3$  AE, with the following exceptions

- Symptomatic adverse events such as nausea, vomiting and diarrhea will not be considered dose limiting if they can be reduced to less than grade 3 within 72 hours with standard supportive measures such as antiemetics and antidiarrheals.
- Asymptomatic Grade 3 electrolyte abnormalities which can be corrected by optimal supplementation.

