#### 15.5.6 Clinical Laboratory Parameters

Descriptive statistics for clinical laboratory values in International System of Units (SI units) and changes from baseline at each assessment time point will be presented by dose level for each clinical laboratory parameter.

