### **14 SUMMARY OF CHANGES FROM THE PROTOCOL**

No changes from the protocol were made in this analysis plan.

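### SAP 10.4 limits all laboratory summary tables to 11 analytes, omitting 16 of the 27 blood tests in protocol Table 10 (including GGT and every electrolyte) and urinalysis, against protocol 15.5.6 and with no change declared

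*SAP*

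**What the plan says.** Protocol 12.7 points to Table 10 for the laboratory parameters to be measured. Protocol 15.5.6 then says that values and "changes from baseline at each assessment time point will be presented by dose level for each clinical laboratory parameter". It excludes no analyte.

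SAP 10.4 opens just as broadly: values and changes for "continuous hematology panel, lipid panel, comprehensive metabolic panel, and urinalysis parameters will be summarized by analyte". Later in the same paragraph it narrows this: "The following analytes will be considered for all summary tables described within this section". The list that follows is hemoglobin, then total white "blood cell (WBC), WBC differential, platelets, alkaline phosphatase (ALP), ALT, AST, bilirubin, creatinine, total cholesterol, and triglycerides". The section goes on to promise CTCAE shift tables, and by-subject listings of laboratory parameters and shifts.

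The opening of protocol section 15 gives the SAP priority where the two documents differ. SAP 14 states: "No changes from the protocol were made in this analysis plan".

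**The concern.** Safety and tolerability are part of the primary objective in both parts of the study. By-dose summaries of laboratory values are meant to show a gradual, dose-related shift that no single result makes obvious. The restricting sentence covers all tables in SAP 10.4, so both the descriptive tables and the shift tables shrink to the list.

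GGT is the most notable absence. The protocol measures five liver function tests, and the SAP tabulates the other four and gives no reason for leaving this one out. The nonclinical summary in protocol 6.2 says: "In dogs, the bile duct and gall bladder were additional target organs". The electrolytes, glucose, blood urea nitrogen, albumin, uric acid and LDH are also absent.

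The section is inconsistent as well. It promises metabolic-panel and urinalysis summaries and then supplies a list with one metabolic-panel test and no clear urinalysis item. It also promises counts for categorical laboratory results, yet the listed analytes are ordinarily continuous. A programmer cannot carry out the whole section as worded.

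**Working it through.** The documents state no analyte count, so there is no plan figure to reproduce. The check compares two lists: protocol Table 10 and the analytes named in SAP 10.4.

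| Table 10 group | In Table 10 | Kept in SAP 10.4 | Omitted |
|---|---|---|---|
| Hematology | 7 | 4 (hemoglobin, WBC, WBC differential, platelets) | 3 (hematocrit, red blood cells, reticulocytes) |
| Metabolic panel | 13 | 1 (creatinine) | 12 (glucose, sodium, potassium, calcium, chloride, carbon dioxide, phosphorus, blood urea nitrogen, uric acid, LDH, albumin, total protein) |
| Lipids | 2 | 2 | 0 |
| Liver function | 5 | 4 (ALP, ALT, AST, bilirubin) | 1 (GGT) |
| Blood total | 27 | 11 | 16 |
| Urinalysis | 10 | none identifiable | 10 |

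- Blood tests in Table 10: 7 + 13 + 2 + 5 = 27.
- Kept: 4 + 1 + 2 + 4 = 11.
- Omitted: 27 - 11 = 16, and 16/27 = 59%.
- Make-up of the 16: GGT (1) + electrolytes (6: sodium, potassium, calcium, chloride, carbon dioxide, phosphorus) + others (9: hematocrit, red blood cells, reticulocytes, glucose, blood urea nitrogen, uric acid, LDH, albumin, total protein).
- If calcium and phosphorus are not counted as electrolytes, the split is 1 + 4 + 11. The total is still 16.

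Counting rules: WBC differential is one entry. Reflex direct bilirubin and reflex urine microscopy are not counted. Bilirubin in the SAP list is read as serum total bilirubin because it follows the liver enzymes, although Table 10 also has a urine bilirubin.

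The omitted tests can still surface in two places:

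- **Listings.** SAP 10.4 lists laboratory parameters by subject, and SAP 6.6 puts all collected data in listings unless otherwise noted.
- **Adverse event tables.** Under protocol 12.7, an abnormal result that meets the investigator's criteria for clinical significance is recorded as an adverse event. If it is treatment-emergent, SAP 10.1 tabulates it by system organ class and preferred term.

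A by-dose shift in an omitted analyte that the investigator does not judge clinically significant therefore appears only in the listings.

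**The case against.** There are fair points on the other side.

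- **The SAP may narrow the tables.** The protocol gives it priority, and key-analyte tables can be a reasonable choice. This stands as to procedure. It does not explain the undeclared departure or the contradiction within SAP 10.4. If the list was meant only as a minimum, the wording still has to say so.
- **The list largely follows the main toxicities.** Protocol 6.2 puts the primary toxicities in bone marrow and lymphoid tissue and expects blood-count changes to come before serious biliary toxicity. The main blood counts are kept. This weakens the argument from the dog findings but does not explain why only GGT is left out of the liver tests.
- **Small groups make listings workable.** Part A has up to 6 subjects per dose level and Part B 14 per cohort. That limits the loss. Part A as a whole is about 64 subjects, however, and comparing dose levels from listings is what the promised summaries would spare the reader.
- **The percentage weights all tests equally.** Hematocrit counts the same as potassium. That is true, and the 59% describes coverage, not clinical importance.

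A reader might go further and infer that biliary and metabolic toxicity is never tabulated. The documents do not support that. ALP, bilirubin, creatinine, cholesterol and triglycerides stay in the value, change and shift tables, and clinically significant abnormalities in any analyte can reach the adverse event tables.

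A reader might also infer that the omission undermines the DLT assessment, since protocol 8.5.3 mentions electrolytes. It does so only in an exception: "Asymptomatic Grade 3 electrolyte abnormalities which can be corrected by optimal supplementation". DLTs come from graded adverse events and are listed by subject under SAP 11.1. They are not read from the laboratory tables.

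**Conclusion.** The SAP omits from its laboratory tables 16 of 27 blood tests, including GGT and all electrolytes, and every identifiable urinalysis item. This conflicts with protocol 15.5.6 and with the first sentence of SAP 10.4, and SAP 14 does not disclose it. Because the SAP governs, the promised by-dose summaries of those tests would not be produced.

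The practical loss is moderate: value and change-from-baseline summaries for the omitted tests, and shift tables for those with CTCAE grades. Protocol 15.5.6 itself promises only the first two, and the shift tables are the SAP's own addition. No data are lost.

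The conclusion rests on reading the list as closed, which is the plain sense of a sentence that governs all the section's tables, and on the counting rules given above.

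**What to change.** Replace the restricting sentence in SAP 10.4 with a statement that the descriptive and change-from-baseline tables cover all parameters in protocol Table 10, and name the liver function tests explicitly, including GGT. Deleting the sentence is not enough. The opening sentence names the hematology, lipid, metabolic and urinalysis panels but no liver function panel, so deletion would not restore GGT and would remove the only mention of ALP, ALT, AST and bilirubin in the section.

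Apply the shift tables to every analyte that has CTCAE grades, including GGT and the electrolytes where graded. The protocol does not reproduce the CTCAE, so the team should check which analytes qualify. If a shorter list is kept for any table, give the reason and record it in SAP 14.

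The cost is SAP wording and additional rows in tables already planned. All the data are already collected under the protocol.

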### **6.3 Summary of Clinical Studies and Known Risks and Benefits**

This is the first study in humans. There are no known clinical benefits associated with ASN002. As of 09 February 2017, a total of 27 patients had been treated in Part A of this study at doses of 10 – 75 mg twice daily (22 patients), and 80 mg once daily (5 patients). Nineteen patients have solid tumors and 8 have non-Hodgkins' lymphomas of various histologies. Accrual and clinical evaluation of ASN002 is ongoing.

At the cut-off date, 21 patients discontinued treatment, mostly (13/21) due to disease progression.

Overall 24 patients (89%) experienced at least one treatment-emergent adverse event (TEAE), and drug-related TEAEs occurred in 44% of patients. Considering TEAE of all causality, the most commonly involved system organ classes, were gastrointestinal disorders (52% of patients), general disorders and administrative site conditions (44%), nervous system disorders (37%), infections and infestations (30%), and investigations, psychiatric and skin disorders (22% each). Infections and infestations, including events of any severity and causality, appear more common at higher doses, with 1/10 patients (10%) at doses  $\leq$ 60 mg daily compared with 7/17 (41%) of patients at doses  $\geq$ 80 mg daily experiencing infectious events. This finding is not unexpected based on experience with other JAK inhibitors.

Individual TEAE occurring in  $>$  10% of subjects, regardless of causality, were chills (5 patients, 19%); anemia, headache, pyrexia, and vomiting (4 patients each, 15%); abdominal pain,

constipation, diarrhea, nausea, small intestine obstruction, fatigue, dehydration, dizziness, anxiety and alopecia, (3 patients each, 11%).

Eleven patients (41%) developed serious adverse events (SAE) and 5 died on study, none of these events were considered to be related to study medication.

No clinically significant abnormalities were noted on ECGs during the study, as of the data cutoff. Hematologic changes, expected based on the preclinical toxicology studies, have usually been mild to moderate at the dose levels tested, but severe anemia, neutropenia, lymphopenia and thrombocytopenia has been observed. Post-treatment white blood cell counts tended to return towards baseline, indicating reversibility of myelosuppression.

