### 12.7 Clinical Laboratory Determinations

The investigator will review all abnormal lab results for clinical significance. Any abnormal clinical laboratory test result meeting the investigator's criteria for clinical significance will be recorded as an AE or SAE as appropriate (see section 12.1.1, Adverse Events, and section 12.1.2, Serious Adverse Events).

Clinical laboratory parameters that will be measured in this study are listed in **Table 10**.

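### As worded, the CTCAE laboratory shift summary in SAP 10.4 has no category for worsening of two or more grades, and no other planned table counts Grade 3 or 4 laboratory values by cohort independently of investigator judgement

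*SAP*

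**What the plan says.** SAP 10.4 (Laboratory Evaluations) plans three kinds of laboratory output.

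- **Descriptive statistics.** Continuous values and changes from baseline are summarized "using descriptive statistics (mean, median, SD, minimum, maximum, and number of subjects". Categorical evaluations get counts and percentages at each level of the analyte. CTCAE grade is not mentioned there.
- **Shift summaries.** Shifts from baseline are graded by CTCAE v4.0 and "presented by analyte, assessment, and treatment cohort". The content is then specified: numbers and percentages of subjects with enough data to evaluate "new Grade 1 abnormalities (i.e., normal at baseline) and shifts of one Grade higher relative to baseline".
- **Listings.** "Data listings for laboratory parameters and shifts will be presented by subject".

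Cytopenias are in scope. The sentence on coverage begins "The following analytes will be considered for all summary tables described within this section: hemoglobin, total white" and goes on to include the white cell differential and platelets.

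Protocol 15.5.6 adds no graded table. It plans "Descriptive statistics for clinical laboratory values in International System of Units (SI units) and changes from baseline at each assessment time point" by dose level. On reporting, Protocol 12.7 says: "Any abnormal clinical laboratory test result meeting the investigator's criteria for clinical significance will be recorded as an AE or SAE as appropriate".

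On background, Protocol 6.3 reports that hematologic changes were usually mild to moderate at the doses tested, but that "severe anemia, neutropenia, lymphopenia and thrombocytopenia has been observed".

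**The concern.** The two named categories describe small movements: normal to Grade 1, and one step up from baseline. A subject who goes from a normal platelet count to Grade 4 thrombocytopenia fits neither. The largest deteriorations are therefore the ones for which the summary has no place.

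The summary is also built visit by visit against baseline. A subject who is counted at one visit for a one-grade shift and then worsens further drops out of the count at the later visit. In the table, deepening toxicity can look like recovery.

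At stake is the description of laboratory toxicity by cohort. Safety and tolerability are primary objectives in both parts (Protocol 7.1). The drug's main nonclinical toxicities were in bone marrow and lymphoid tissue (Protocol 6.2). Cumulative hematologic toxicity at 120 mg QD was among the reasons given for the Part B dose (Protocol 6.4.3).

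**Working it through.** The plan states no figure to reproduce. The check is a count of table cells, followed by a search for another output that would fill the gap.

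**Step 1: possible worsening shifts.** Inputs are Grade 0 (normal) to Grade 4 at baseline and at a post-baseline visit. A worsening shift is any pair with the later grade higher.

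- From Grade 0: 4; from Grade 1: 3; from Grade 2: 2; from Grade 3: 1.
- Total: 4 + 3 + 2 + 1 = 10.

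**Step 2: shifts covered by the two categories as worded.**

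- New Grade 1 from normal: 0-1.
- One grade above baseline: 0-1, 1-2, 2-3, 3-4.
- Together: 4 distinct cells.
- Not covered: 10 − 4 = 6 cells, namely 0-2, 0-3, 0-4, 1-3, 1-4, 2-4.

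**Step 3: shifts ending at Grade 3 or 4.**

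- Ending at Grade 3: 0-3, 1-3, 2-3. Ending at Grade 4: 0-4, 1-4, 2-4, 3-4. Total: 3 + 4 = 7.
- Covered: 2-3 and 3-4. Not covered: 7 − 2 = 5.

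**Step 4: effect of the per-visit layout.** Blood counts are scheduled on Days 8 and 15 of Cycle 1 (schedules of assessments, both parts). Take a subject who is Grade 0 at baseline, Grade 1 on Day 8 and Grade 3 on Day 15.

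| Visit | Shift from baseline | Counted? |
|---|---|---|
| Day 8 | 0-1 | Yes |
| Day 15 | 0-3 | No |

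**Step 5: does another output count subjects by laboratory grade?**

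| Output | What it gives | Fills the gap? |
|---|---|---|
| Descriptive statistics (SAP 10.4, Protocol 15.5.6) | Per-visit minimum or maximum, not a count by grade | No |
| Categorical laboratory summary (SAP 10.4) | Counts by analyte level, with no mention of CTCAE grade | Not clearly |
| Shift listing (SAP 10.4) | Every shift by subject, no incidence | No |
| TEAEs by term, relationship and intensity (SAP 10.1) | Counts by cohort, but only of results the investigator judged clinically significant (Protocol 12.7) | Only through investigator judgement |
| DLT listing (SAP 11.1) | Part A only, by subject, only events meeting DLT criteria | No |

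A severe cytopenia leaves traces in several places. No planned table counts it by cohort from the laboratory value alone.

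**The case against.** The strongest reply is that the SAP sentence is loosely drafted, not restrictive. It does not say that these are the only categories, and the sentence before it commits in general terms to evaluating shifts by CTCAE. One Grade higher could be shorthand for at least one grade higher, in which case all 10 worsening cells are counted and none is missed. Redundancy does not settle the matter, because the new-Grade-1 row is contained in the second row under either reading.

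That much is fair: intent cannot be established, and a reader should not infer a decision to leave severe shifts out. But the words for the broader reading are not in the text, and a programmer following the text would count 4 cells. Even on the broader reading, a 0-4 shift shares a count with 0-1 shifts, so severe changes are still not shown. Both readings need an edit.

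It can also be said that the cohorts are small (up to 6 subjects per dose level in Part A, up to 14 per cohort in Part B), so listings are readable. No dose decision depends on this table: the safety review committee sees adverse events and laboratory data after each cohort, and the MTD rests on DLTs. Both statements are correct. They keep this a reporting defect and not a threat to dose escalation, but a listing still leaves the reader to work out the incidence.

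**Conclusion.** The point holds for the shift summary as worded: 6 of 10 worsening cells are uncounted, including 5 of the 7 that end at Grade 3 or 4. It rests on the literal reading of one sentence and on Grades 0 to 4 as the scale. It is worth correcting, because the table as specified would mislead on the toxicity this drug is expected to produce and the correction is cheap.

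Three stronger conclusions that a reader might draw are not supported.

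- **That severe laboratory toxicity goes unreported.** It remains in the listings and the per-visit extremes, in the TEAE-by-intensity table if reported, and in the Part A DLT listing if it meets the criteria. What is missing is a count by cohort that does not depend on investigator judgement.
- **That hematologic toxicity determined the Part B dose.** Protocol 6.4.3 gives three supports: a pneumonia SAE/DLT at 100 mg BID, cumulative hematologic toxicity at 120 mg QD, and a pneumonitis SAE. It was one of the three.
- **That 6 of 10 is a share of patients or events missed.** It counts table cells. The documents give no distribution of baseline or on-study grades, so the number of subjects affected cannot be estimated.

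**What to change.** Replace the sentence in SAP 10.4 with a table of baseline grade against worst post-baseline grade for each listed analyte and each cohort, plus the number and percentage of subjects with a new Grade 3 or higher value. Using the worst post-baseline grade also removes the drop-out between visits shown in Step 4.

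At minimum, change the second category to one or more Grades higher and show shifts to Grade 3 or 4 on a separate line.

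In the same edit, cite CTCAE 4.03 in place of v4.0, to match Protocol 8.5.3 and 12.4 and SAP 2.3.2. This is alignment only; no effect on any laboratory grade has been shown.

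The cost is a wording change and one standard table from data already collected. It should be settled before database lock. Sample size, visits and the DLT rules are untouched.

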### 15.5.4 Adverse Events

The Medical Dictionary for Regulatory Activities (MedDRA, version 17.0 or higher) will be used to code AEs.

An AE (classified by preferred term) that started during the treatment period will be considered a TEAE if it was not present prior to the first dose of study drug, or was present prior to the first dose of study drug but increased in intensity during the treatment period. If more than 1 AE is reported prior to the first dose of study drug and coded to the same preferred term, then the AE with the least intensity will be used as the benchmark for comparison to the AEs occurring during the treatment period which were also coded to that preferred term. Any AE present prior to the first dose of study drug that increases in intensity during the treatment period will be re-entered with a new start date of the date of increased intensity. An AE that occurs more than 30 days after the last dose of study drug will not be counted as a TEAE.

Descriptive statistics (the number and percentage) for subjects reporting TEAEs will be tabulated by system organ class, preferred term, and dose level. If more than 1 AE is coded to the same preferred term for the same subject, the subject will be counted only once for that preferred term.

The incidence of TEAEs by severity and relationship to study drug will be summarized by system organ class, preferred term, and dose level. If more than 1 AE is coded to the same preferred term for the same subject, the subject will be counted only once for that preferred term using the most severe and most related occurrence for the summarization by severity and by relationship to the study drug respectively. The incidence of TEAEs will also be summarized by preferred term and dose level and sorted by decreasing frequency. SAEs and AEs leading to premature discontinuation of study drug will be summarized by preferred term and dose level, and sorted by decreasing frequency for dose level.

Descriptive statistics (the number and percentage) for subjects reporting TEAEs will be tabulated by system organ class, preferred term, and dose level. If more than 1 AE is coded to the same preferred term for the same subject, the subject will be counted only once for that preferred term.

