## **7.2 Visit Windows**

The screening assessments and the treatment/post-treatment assessments will be partitioned into the following two visit windows:

- A screening window, beginning on Day -28 and ending on Day -1.
- A treatment window, beginning on Day 1 of Cycle 1 and ending on the Study Day (see [Section 7.3](#)) corresponding with the End of Treatment visit.

Subject visits for all parts of the study (i.e., Part A, and Part B) will be presented according to the nominal visit as obtained upon the CRF. All values will be included in the subject data listings.

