#### **10.1 Adverse Events**

Treatment emergent adverse events (TEAE) will be classified into a standardized terminology using the Medical Dictionary for Regulatory Activities (MedDRA, version 17.0 or higher) system organ classifications and preferred terms. All summaries of the incidence of treatment-emergent adverse events will be provided using the Safety Population by treatment cohort and overall. Although a preferred term or system organ class may be reported more than once for a subject, each subject will only be counted once in the incidence count for that preferred term or system organ class. Summaries of the following types will be provided:

- Summary of treatment-emergent adverse events;
- Summary of treatment-emergent adverse events by MedDRA system organ class and MedDRA preferred term;
- Summary of treatment-emergent adverse events by MedDRA system organ class, MedDRA preferred term, relationship to study drug, and intensity;

- Summary of serious treatment-emergent adverse events leading to discontinuation from the study by MedDRA preferred term, sorted alphabetically by system organ class and preferred term;
- Summary of treatment-emergent adverse events leading to discontinuation from the study by MedDRA preferred term, sorted alphabetically by system organ class and preferred term.

These summaries will present the number and percentage of subjects reporting an adverse event for each classification level. The denominators for calculating the percentages will be based on the number of exposed subjects in the Safety population (i.e., study drug was administered) in the treatment cohort summarized.

Listing of subject dropouts due to AEs prior to post-dose tumor assessment will be generated. All adverse events, serious adverse events and deaths, and adverse events leading to discontinuation from the study will also be provided in data listings by subject.

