# **11 OTHER ANALYSES**

## **11.1 Dose Escalation Safety Analyses**

The study will include multiple safety analyses for the dose escalation component (Part A). Each treatment cohort is viewed as a separate safety analysis, insofar as the safety review committee will decide whether the dose escalation will continue to the next planned (or intermediate) dose level, if additional subjects will be added to the current dose level, or if the dose escalation will be stopped. The safety review committee can also terminate the study due to safety concerns. Each review will be conducted with the latest available data.

---

A data listing of dose-limiting toxicities (DLTs) for Part A will be presented by subject.

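### SAP 10.4 tabulates CTCAE laboratory shifts only visit by visit and without the grade reached, so no planned laboratory table gives the share of subjects who ever reached Grade 3-4 cytopenia on measured counts

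*SAP*

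**What the plan says.** SAP 10.4 plans four kinds of laboratory output:

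- descriptive statistics (including the minimum) of values and changes from baseline, by analyte, assessment and cohort;
- counts of subjects at each level of categorical analytes, which the text does not equate with CTCAE grades;
- CTCAE v4.0 shifts from baseline, "presented by analyte, assessment, and treatment cohort", with summaries of "new Grade 1 abnormalities (i.e., normal at baseline) and shifts of one Grade higher relative to baseline";
- listings: "Data listings for laboratory parameters and shifts will be presented by subject".

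SAP 7.2 adds that visits are "presented according to the nominal visit as obtained upon the CRF". Protocol 15.5.6 and the Safety Analyses part of the protocol synopsis also summarize laboratory results by time point. Neither adds a worst-grade or Grade 3-4 table.

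Two outputs outside the laboratory section bear on the same question. SAP 10.1 plans a "Summary of treatment-emergent adverse events by MedDRA system organ class, MedDRA preferred term, relationship to study drug, and intensity", and Protocol 15.5.4 counts each subject once per preferred term, "using the most severe and most related occurrence for the summarization by severity and by relationship to the study drug respectively". A laboratory result enters that route only under Protocol 12.7: a result that meets the investigator's "criteria for clinical significance will be recorded as an AE or SAE as appropriate". SAP 11.1 adds: "A data listing of dose-limiting toxicities (DLTs) for Part A will be presented by subject".

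**The concern.** Safety and tolerability are a primary objective in both parts. Protocol 6.2 names bone marrow and lymphoid tissue as the main nonclinical toxicity targets. Protocol 6.3 reports that hematologic changes in Part A were usually mild to moderate, but that severe anemia, neutropenia, lymphopenia and thrombocytopenia have occurred. Protocol 6.4.3 cites cumulative hematologic toxicity at 120 mg QD among the observations behind the 75 mg BID dose for Part B.

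For such a drug, a reader of the study report will look for the share of subjects in each cohort whose measured counts ever fell to Grade 3 or 4, set against their grade at entry. The plan grades the values but stops short of that summary. It would have to be counted from listings afterwards, with no pre-specified rule on which samples count.

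**Working it through.** The plan states no figure on this point, so there is none to reproduce. The check sets each planned output against the quantity wanted: per cohort, the number of subjects whose worst measured post-baseline count was Grade 3 or 4.

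| Planned output | Counts subjects over the whole course? | Shows grade reached? | Rests on measured counts alone? |
|---|---|---|---|
| Descriptive statistics (SAP 10.4) | No, per assessment | No; the minimum shows the lowest value, not how many subjects were low | Yes |
| CTCAE shift summaries (SAP 10.4) | No, per assessment | No | Yes |
| Listings of values and shifts (SAP 10.4) | No summary; counted by hand | Derivable from the values | Yes |
| TEAEs by intensity (SAP 10.1, Protocol 15.5.4) | Yes | Yes | No, needs investigator judgement (Protocol 12.7) |
| DLT listing (SAP 11.1) | Listing, Part A only | Only for events meeting the DLT definition | No |

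No row meets all three requirements as a summary.

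**Shift categories.** There are two ways to read the second category.

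1. Strict: exactly one Grade above baseline. A subject who goes from normal to Grade 3, or from Grade 1 to Grade 4, is then in neither category.
2. Loose: at least one Grade above baseline. That subject is now counted, but in the same cell as one who moved from normal to Grade 1. The grade reached is still not shown.

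The Grade 3-4 share is unavailable under both readings, so the conclusion does not depend on which was meant.

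**By-assessment layout.** Suppose a Grade 3-4 row were added at each visit, which is not planned. Let r_j be the number of affected subjects at visit j and n the cohort size. The number ever affected, E, then satisfies only

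max(r_j) ≤ E ≤ min(n, sum of r_j).

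The lower end applies if the same subjects are affected each time, the upper end if they differ. Visit rows alone cannot say which, so a subject-level table is needed.

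**How many rows.** Protocol Table 2 schedules Part B blood counts after baseline on Cycle 1 Days 8 and 15, on Days 1 and 15 of each later cycle, at End of Treatment and at 30-day follow-up. Over c cycles that is 2 + 2(c − 1) + 1 + 1 = 2c + 2: 8 for c = 3, 14 for c = 6 and 26 for c = 12. The number of cycles is an assumption; the protocol limits treatment to 12 months and names Cycle 12 as the last PK sampling cycle.

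**DLT route.** The hematologic DLT definition (Protocol 8.5.3) covers Grade 4 neutropenia or thrombocytopenia lasting more than 7 days after the last dose, febrile neutropenia, and Grade 3 or higher thrombocytopenia with bleeding, all within Cycle 1. Shorter severe neutropenia and later cumulative toxicity fall outside it.

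**The case against.** The strongest reply is that a subject-level Grade 3-4 count already exists in the adverse-event table by intensity. The protocol bounds investigator judgement fairly closely. Section 12.1.1 includes clinically relevant laboratory abnormalities among AEs, Section 12.1.2 gives blood dyscrasias as an example of an important medical event, and Section 12.4 describes Grade 3 as severe or medically significant. Many Grade 3-4 cytopenias should therefore be reported. This stands as partial cover. It does not replace a table from measured counts: subjects may enter with neutrophils from 1000/µL, platelets from 75,000/µL and hemoglobin from 8 g/dL with transfusion support (Protocol 9.1), and whether a further fall is clinically significant could plausibly be judged differently between sites.

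Second, the SAP says what the shift summaries will contain, not that they contain nothing else, and one Grade higher may mean at least one. That is a fair reading. A reader might count the grade-to-grade moves that the strict wording misses and take the result as the size of the problem. The documents do not support that: the count disappears under the loose reading, and it treats all moves alike without saying how many subjects make them.

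Third, cohorts are small, the listings are complete and the safety review committee sees laboratory data directly (Protocol 8.5.1). Hand counting is feasible, and the 120 mg QD toxicity was recognised without this table. All true; it limits the consequence.

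Fourth, Protocol 15.5.6 promises only descriptive statistics, so the SAP contradicts nothing and already goes further. Also true: this is an improvement to the summary, not a breach of the protocol.

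**Conclusion.** The point holds as a gap in the planned laboratory summaries. SAP 10.4 gives shifts per assessment, in categories that hide the grade reached, and no other laboratory table in either document supplies the share of subjects who ever reached Grade 3-4 cytopenia on measured counts. This rests on the text alone and holds under both readings of the shift wording.

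No numerical size can be given. The documents contain no graded incidence of measured cytopenias, and how far the AE table would fall short of a count-based table depends on investigator reporting that cannot be known in advance.

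A reader might infer that severe cytopenias would go unreported or that the dose decision was compromised. Neither follows. Every value and shift is listed by subject, clinically significant falls become AEs tabulated by intensity, and Part A DLTs are listed. Dose escalation and the Part B response test do not use these tables. The change should be made because it is cheap and serves a primary objective, not because the trial's conclusions are at risk.

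**What to change.** In SAP 10.4, make two changes.

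1. Add one table per treatment cohort (in Part B, per disease cohort) of baseline CTCAE grade against worst post-baseline grade, 0 to 4, for hemoglobin, WBC, neutrophils, lymphocytes and platelets, graded in the low direction. State that all scheduled, unscheduled and 30-day follow-up samples count. The Grade 3 and Grade 4 columns then give the share wanted, with the grade at entry visible beside it.
2. Reword the by-assessment category so that it covers shifts of one or more Grades above baseline.

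The cost is one extra table and a few words. The scheduled samples are already planned, so no visits or subjects are added. The AE table by intensity stays as it is; the two can then be read side by side.
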